6.5.4.1 Hematology

Hemoglobin, hematocrit, red blood cell count, white blood cell count with differential (neutrophils including bands, lymphocytes, monocytes, eosinophils, basophils) and platelet count will be measured at all scheduled study visits, within the visit window specified in [Table 6-1](#).

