Subjects from the CAIN457A2304 maintenance period will continue the treatment regimen and dose that they were assigned to (Fixed interval regimen or Retreatment at start of relapse regimen) during the maintenance treatment period of the core study and return for visits every four weeks up until Week 156. Subjects and study personnel will remain blinded during the first two years of the treatment period (except for patients in the open label part of the study). The last blinded dose of the treatment period is administered at Week 152.

At Week 156, subjects will be unblinded and will have the option (based on investigator judgment) to switch dosing regimens, with the specific options depending on the blinded treatment assigned until that point. Generally, subjects may switch off of the SoR treatment regimen to active secukinumab treatment every four weeks, and subjects may switch from secukinumab 150 mg s.c. to secukinumab 300 mg s.c. After Week 156, office visits will only be required every 12-16 weeks until Week 260 (End of Treatment period for CAIN457A2304E1) unless a subject continues with the SoR treatment regimen. Specific details of the open-label treatment options for unblinded subjects starting at Week 156 are described in Section 5.2 and in Table 5-1.

Subjects from the CAIN457A2307 maintenance period will continue in the treatment regimen and dose that they received during the CAIN457A2307 maintenance treatment period (i.e., 300 mg sc secukinumab every four weeks), and return for visits every four weeks up until Week 156. After Week 156, subjects will continue being treated every four weeks, but will only be required to come in for office visits every 12-16 weeks. These subjects were treated open-label during the core study, and will continue to be treated open-label during the treatment period of CAIN457A2304E1. The last dose of secukinumab is provided at Week 256, four weeks prior to the end of the treatment period.

Please refer to [Section 5.2](#) for a more detailed description of the treatment arms.

Subjects who discontinue study treatment prematurely during the treatment period should have all Week 260 protocol assessments (EOT) performed approximately four weeks after their last dose of secukinumab/secukinumab placebo and then enter the treatment-free follow-up periods (follow-up period and follow-up 2 period).

Follow-up period (for all subjects)

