	160	164	168	172	176	180	84	188	192	196	200	204	208	212	216	220	224	228	232	236	240	244	248	252	256	260		264 /F4	268 /F8		
Week (Relative to Baseline of core studies)																															
Visit Window (in days)	±5	±5	±5	±5	±5	±5	±5	±5	±5	±5	±5	±5	±5	±5	±5	±5	±5	±5	±5	±5	±5	±5	±5	±5	±5	±5	±5				
Days	1121	1149	1177	1205	1233	1261	1289	1317	1345	1373	1401	1429	1457	1485	1513	1541	1569	1597	1625	1653	1681	1709	1737	1765	1793	1821					
In office visit if every 4 wks dosing			X			X			X				X			X			X			X							X	X	
Home administration if every 4 wks dosing	X	X		X	X		X	X		X	X	X		X	X		X	X		X	X		X	X	X						
In office visit if SoR dosing	X	X	X	X	X	X	X	X	X	X	X	X	X	X	X	X	X	X	X	X	X	X	X	X	X	X	X	X			
Concomitant medications	X	X	X	X	X	X	X	X	X	X	X	X	X	X	X	X	X	X	X	X	X	X	X	X	X	X	X	X			
Physical examination			X			X			X			X			X			X			X						X	(X)	X	X	
Weight																												X		X	
Vital signs	O	O	x	O	O	x1	O	O	x	O	O	O	x	O	O	x	O	O	x	O	O	x	O	O	O	x	O	x	x	x	
Urinalysis (local)			X			X			X			X			X			X			X						X		X		
Lab analysis: chemistry and hematology ²						X							X						X								X	X	X	X	
Fasting Labs: lipid panel ²																											X			X	
Fasting Labs: plasma glucose ²						X							X					X								X			X		

	Treatment Period (Years 3 and 4)																										Unscheduled visit ¹¹	Follow-up period	Follow-up 2 Period
	160	164	168	172	176	180	84	188	192	196	200	204	208	212	216	220	224	228	232	236	240	244	248	252	256	260			
Week (Relative to Baseline of core studies)	160	164	168	172	176	180	84	188	192	196	200	204	208	212	216	220	224	228	232	236	240	244	248	252	256	260			
Visit Window (in days)	±5	±5	±5	±5	±5	±5	±5	±5	±5	±5	±5	±5	±5	±5	±5	±5	±5	±5	±5	±5	±5	±5	±5	±5	±5	±5			
Days	1121	1149	1177	1205	1233	1261	1289	1317	1345	1373	1401	1429	1457	1485	1513	1541	1569	1597	1625	1653	1681	1709	1737	1765	1793	1821			
Serum pregnancy test ³																													
Urine pregnancy test (local) ⁴			x			x			x				x			x			x			x			x				
ECG (standard 12 lead)						x							x				x								x				
Blood sample for IG ^{5,6}													x												x	x ^{5,6}			
Blood sample for PK ^{5,6}													x												x	x ^{5,6}			
PASI	o	o	x	o	o	x	o	o	x	o	o	o	x	o	o	x	o	o	x	o	o	x	o	o	o	x	x	x	x
Assessment of rebound symptoms ⁷																									x	x ⁷	x	x	
IGA mod 2011			x			x			x				x			x			x			x			x	x	x	x	
Adverse event (AE) assessment	o	o	x	o	o	x	o	o	x	o	o	o	x	o	o	x	o	o	x	o	o	x	o	o	o	x	x	x	
DLQI			x			x			x				x			x			x			x			x				

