HAQ-DI ⁸			x			x			x				x			x			x			x			x				
Serious AE assessment	o	o	x	o	o	x	o	o	x	o	o	o	x	o	o	x	o	o	x	o	o	x	o	o	o	x	x	x	
Complete PASI (and IGA ⁹) eCRF and call IRT	o	o	x	o	o	x	o	o	x	o	o	o	x	o	o	x	o	o	x	o	o	x	o	o	o	x	x	x	

	Treatment Period (Years 3 and 4)																										Unscheduled visit ¹¹	Follow-up period	Follow-up 2 Period
	160	164	168	172	176	180	84	188	192	196	200	204	208	212	216	220	224	228	232	236	240	244	248	252	256	260			
Week (Relative to Baseline of core studies)	160	164	168	172	176	180	84	188	192	196	200	204	208	212	216	220	224	228	232	236	240	244	248	252	256	260			
Visit Window (in days)	±5	±5	±5	±5	±5	±5	±5	±5	±5	±5	±5	±5	±5	±5	±5	±5	±5	±5	±5	±5	±5	±5	±5	±5	±5	±5			
Days	1121	1149	1177	1205	1233	1261	1289	1317	1345	1373	1401	1429	1457	1485	1513	1541	1569	1597	1625	1653	1681	1709	1737	1765	1793	1821			
Dispense Investigational Treatment ¹⁰	O	O	x	O	O	x	O	O	x	O	O	O	x	O	O	x	O	O	x	O	O	x	O	O	O	x			
End of Treatment Period (EOT) eCRF and call IRT																											x		
Follow-up Period completion eCRF																											x		
Follow-up 2 Period completion eCRF																											x		

eCRF:electronic case report form; PK:pharmacokinetics; IG:immunogenicity

O: assessment completed for subjects with protocol-mandated in-office visits in between Week 160 and 256.

*The screening period will be the duration between signing the informed consent form and enrollment registered with Interactive response technology (IRT). Subjects must sign the informed consent form after completing the core study Week 52 assessments.

^aEnrollment into the extension study occurs on the same day (Week 52) as the end of maintenance period of the core study CAIN457A2304 or CAIN457A2307 (±5 days). The column for Week '52 core' represents assessments that will be done during the CAIN457A2304 core Week 52 visit or the CAIN457A2307 Week 40 visit. These assessments will be entered in the core study eCRFs. The column Week '52 ext' represents assessments that will be done for the CAIN457A2304E1 study.

¹These assessments are supported by and are stored with the source documentation. However, data regarding to which Inclusion/Exclusion criteria are not met are captured on the Inclusion/Exclusion Screen eCRF.

²Samples will be shipped to and analyzed by the central laboratory.

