6.5.4.2 Clinical chemistry

Serum chemistries will include urea, creatinine, total bilirubin, AST (SGOT), ALT (SGPT), GGT, alkaline phosphatase, sodium, potassium, bicarbonate, calcium, phosphorous, total protein, albumin, and uric acid. Serum chemistries will be measured at all scheduled study visits within the visit window specified in [Table 6-1](#).

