    - ii. Censored day for Labs will be end of period day (i.e., day 365 for year 1, day 730 for year 1-2, etc.,) for ongoing patients or the last assessment day within each interval.

The MedDRA version used for reporting the adverse events will be described in a footnote. Listings of all adverse events will be done based on entire study period and follow-up 2 period separately. A column indicating if the adverse event is treatment emergent or not will be shown. Non-treatment emergent adverse events may be summarized separately upon request.

Algorithms for date imputations will be provided in RAP M8.

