| Glucose increased (Hyperglycemia ) | ;  | >ULN - 8.9 mmol/L                       | >8.9 - 13.9 mmol/L                 | >27.8 mmol/L          |
| Glucose decreased (Hypoglycemia)   | <LLN - 3.0 mmol/L                        | <3.0 - 2.2 mmol/L                       | <2.2 - 1.7 mmol/L                  | <1.7 mmol/L           |
| Cholesterol high                   |  | >ULN - 7.75 mmol/L                      | >7.75 - 10.34 mmol/L               | >10.34 - 12.92 mmol/L |
| Hypertriglyceridemia               | 1.71 - 3.42 mmol/L                       | >3.42 - 5.7mmol/L                       | >5.7 - 11.4 mmol/L                 | >11.4 mmol/L          |

\*Note: for “creatinine increased” the baseline criteria do not apply

Shift tables will be presented comparing baseline laboratory result (CTCAE grade) with the worst results (expressed in CTCAE grade) during the treatment phase (either initial or entire) analyzed. Of note, baseline will be defined as last assessment prior to first dosing in the core study. Subjects with abnormal laboratory values will be listed and values outside the normal ranges will be flagged.

Exposure adjusted incidence rate for neutropenia CTCAE grade  $\geq 2$  will be presented for the entire treatment period.

Summaries for newly occurring or worsening clinically notable lipid abnormalities will also be provided cumulatively for each of the following parameters and categories:

- HDL:
  - $\leq$ LLN
  - $<0.8 \times$  LLN
- LDL, cholesterol, triglycerides:
  - $\geq$ ULN
  - $>1.5 \times$  ULN
  - $>2.5 \times$  ULN

Subjects with newly occurring or worsening after baseline abnormalities in lipid parameters will be listed. If a subject experiences newly occurring or worsening of abnormality for a parameter the entire time course of that parameter will be listed.

Newly occurring liver enzyme abnormalities will also be summarized based on the event criteria given in [Table 1-19](#).

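### Scheduled hematology and chemistry draws fall from 26 to 4 per 104 weeks at Week 156, and the whole-period laboratory rates count the sparsely sampled years in full

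*Protocol*

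**What the plan says.** **Schedule in the table.** In Protocol Table 6-1 the row "Lab analysis: chemistry and hematology" is marked at each 4-weekly visit through Week 156. For Weeks 160 to 260 it is marked at Weeks 180, 208, 232 and 260, and then in the unscheduled column and at follow-up Weeks 264 and 268. In the copy I read, the right end of this row is displaced by one column; I read the last four marks that way. The table's extra code is defined as "O: assessment completed for subjects with protocol-mandated in-office visits in between Week 160 and 256". This row carries no such code, so by the table every regimen has the same four draws.

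**Schedule in the text.** Protocol 6.5.4.1 says that "platelet count will be measured at all scheduled study visits", and 6.5.4.2 says "Serum chemistries will be measured at all scheduled study visits". Both cite Table 6-1 only for the visit window. Protocol 3.1 says "After Week 156, office visits will only be required every 12-16 weeks until Week 260", except for subjects who stay on the start-of-relapse (SoR) regimen, who attend every 4 weeks.

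**Analysis.** SAP 1.9.1 ends a subject's exposure time on the day a laboratory event is first seen. For subjects without an event, "Censored day for Labs will be end of period day (i.e., day 365 for year 1, day 730 for year 1-2, etc"; this applies to ongoing patients, and others are censored at their last assessment in the interval. SAP 2.4.1 models first occurrences as a Poisson process with constant intensity. SAP 1.9.2 plans exposure-adjusted rates for nested CTCAE grades. It also names one rate individually, "Exposure adjusted incidence rate for neutropenia CTCAE grade" 2 or higher, for the entire treatment period. Nothing in the SAP reports or adjusts for the number of tests.

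**The concern.** Long-term safety is the primary objective. A laboratory abnormality without symptoms is found only if blood is drawn while it lasts. After Week 156 the scheduled draws are 24 to 28 weeks apart, yet the time between them enters the denominator just as it did when draws were 4 weeks apart. A rate that pools the two stretches understates what 4-weekly sampling would have shown. The shortfall comes from the late years, which are the years the extension was lengthened to study. If yearly laboratory rates were produced, a fall after Year 3 could appear with no change in true risk.

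**Working it through.** The documents state no number of laboratory draws and no laboratory-event rate, so there is no planned figure to reproduce.

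**1. Draws by the table.** Weeks 56 to 156 every 4 weeks: (156 − 56)/4 + 1 = 26. Weeks 160 to 260: 4. The ratio is 4/26 = 0.154. Week 156 is Day 1093, inside the third 365-day interval, so the yearly counts since core baseline are 13, 13, 2 and 2 for Years 2 to 5.

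**2. Draws by the text.** All scheduled visits in Weeks 160 to 260 would be 8 for 4-weekly dosing (Weeks 168, 180, 192, 208, 220, 232, 244, 260) and (260 − 160)/4 + 1 = 26 for SoR. Table and text cannot both be followed.

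**3. Scheduled detection.** Take an episode of d weeks with onset uniform over 104 weeks, detected if a draw falls within it. The detection probability is the sum of min(d, gap) over the gaps between draws, divided by 104. Before Week 156 there are 26 gaps of 4 weeks. After it, by the table, the gaps are 24, 28, 24 and 28 weeks. For d = 4 this gives 26 × 4/104 = 1.000 before and 4 × 4/104 = 0.154 after. For d = 24 it gives 1.000 and 4 × 24/104 = 0.923.

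**4. Five-year rate.** Assume 4-weekly sampling in core Year 1 (the core schedule is not in these documents), no dropout, equal person-time per year and a low, constant true rate. With r the ratio from step 3, the rate relative to 4-weekly sampling throughout is (3 + 2r)/5. For d up to 4 weeks: (3 + 2 × 0.154)/5 = 0.66, a dilution of 34%.

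| Assumed duration (weeks) | Detection to Week 156 | Detection after | Ratio r | Five-year dilution |
|---|---|---|---|---|
| 2 | 0.500 | 0.077 | 0.15 | 34% |
| 4 | 1.000 | 0.154 | 0.15 | 34% |
| 8 | 1.000 | 0.308 | 0.31 | 28% |
| 12 | 1.000 | 0.462 | 0.46 | 22% |
| 24 | 1.000 | 0.923 | 0.92 | 3% |
| 28 or more | 1.000 | 1.000 | 1.00 | 0% |

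**5. Yearly rates, if produced.** These were simulated under the SAP's first-detection and full-interval rule, with a constant true onset rate of 5 per 100 subject-years. From Years 2–3 to Years 4–5 the rate goes from about 2.5 to 0.4 for 2-week episodes, 5.0 to 0.8 for 4-week, 5.4 to 1.5 for 8-week and 7.1 to 5.0 for 26-week. Values above 5 arise because one episode can be found in two yearly intervals. With 4-weekly draws kept throughout, the rate for 4-week episodes stays at about 5.

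**The case against.** **The text conflict looks like stale wording.** Protocol 6.5 sends the reader to Table 6-1 for the frequency of assessments, and the disputed sentences match the table up to Week 156. That is fair. A reader might infer that SoR subjects are sampled 26 times against 8 for the others, so that regimens cannot be compared. The documents do not support that: it follows only from the text, and the table gives all regimens the same four draws. What stands is that sites have two instructions for Weeks 160 to 260.

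**The late-against-early fall is not the effect on the planned rate.** For episodes of 2 to 6 weeks the ratio of detection before to after Week 156 is 4.3 to 6.5 (1/0.231 to 1/0.154). It is tempting to read that as the error in the neutropenia rate. But that rate covers the entire treatment period, where the dilution is at most about 1.5-fold (1/0.66) under the assumptions above, and nil for long episodes. Dropout reduces it further. As an illustration, about 108 of 675 subjects (16%) had discontinued by Amendment 1. If Years 4 and 5 each carried 84% of a full year's person-time, the relative rate would be (3 + 1.68 × 0.154)/(3 + 1.68) = 0.70, a dilution of 30%.

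**No waning risk is tabulated.** The yearly summaries that the SAP names are for adverse events, and no by-year laboratory table is listed. This stands, with one qualification: the laboratory censoring rule is itself written by year, so yearly rates may be produced.

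**Other draws count.** Draws at unscheduled visits and at Weeks 264 and 268 within 84 days of the last dose enter the treatment-period summaries and soften the contrast slightly. The analysis is descriptive, with no hypothesis test. Neither point removes the bias in the estimate.

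**Conclusion.** The point holds for hematology and chemistry. By Table 6-1 the scheduled draws fall 6.5-fold at Week 156 in every regimen, and the SAP's exposure-adjusted rates take no account of it. The direction is certain for scheduled draws, because the four late weeks are a subset of a 4-weekly grid and can only find the same events or fewer. The size is conditional on episode duration, which is an assumption: about 34% dilution of the five-year rate for episodes of 4 weeks or less, about 22% for 12 weeks, about 3% for 24 weeks and none from 28 weeks, before any allowance for dropout or extra draws.

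A reader might extend this to all laboratory data. The documents do not support that. Fasting glucose, lipids and urinalysis sit on separate rows of Table 6-1 and were not 4-weekly before Week 156, so the glucose, cholesterol and triglyceride grades in SAP 1.9.2 fall outside the point.

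The conflict between Protocol 6.5.4.1 and 6.5.4.2 and the table is a separate matter of wording, and it needs reconciling whichever instruction the sponsor intended.

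**What to change.** 1. Reconcile Protocol 6.5.4.1 and 6.5.4.2 with Table 6-1 for Weeks 160 to 260 and state which governs. Which schedule is right is the sponsor's decision; this review proposes none.
2. In SAP 1.9.1 and 1.9.2, present the exposure-adjusted rates for neutropenia and the other hematology and chemistry CTCAE grades separately for time up to Week 156 and time after it, beside the whole-period rate. Give the number of scheduled tests per subject in each interval.
3. Optionally, add a sensitivity table that restricts comparisons across years to common draw weeks. It would discard most of the early draws, so it should sit beside the full-data table and not replace it.

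The cost is a wording correction, a few more table columns and smaller event counts in each period. No new data are needed.

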6.5.4.2 Clinical chemistry

Serum chemistries will include urea, creatinine, total bilirubin, AST (SGOT), ALT (SGPT), GGT, alkaline phosphatase, sodium, potassium, bicarbonate, calcium, phosphorous, total protein, albumin, and uric acid. Serum chemistries will be measured at all scheduled study visits within the visit window specified in [Table 6-1](#).

6.5.4.3 Urinalysis

Dipsticks will be provided by the central laboratory to the study sites for local urinalysis assessments. The sites will record the results in the appropriate eCRF page for each subject.

Standard dipstick measurements for specific gravity, protein, glucose, pH, blood, urine blood dipstick (non-hemolyzed), urine blood dipstick (hemolyzed), bilirubin, ketones and WBC will be done at scheduled visits as indicated in [Table 6-1](#).

6.5.4.4 Immunogenicity (IG)

Blood samples for IG (anti-secukinumab antibodies) will be taken pre-dose at the scheduled timepoints as indicated in [Table 6-1](#) and [Table 15-2](#). Blood samples (approximately 2 mL) will be collected into serum separator tubes (SST). The blood sample will be allowed to clot over a minimum of 30 minutes at room temperature prior to harvesting of the serum. The serum will be obtained by centrifugation at approximately 2500 revolutions per minute (rpm) for 10 minutes.

Serum samples will be placed on ice, split into 2 aliquots (labeled plain barrier polypropylene tubes) and then stored (within 30 minutes of collection) at approximately -70°C to -20°C prior to shipment on dry ice to the central laboratory. Shipment of stored aliquots from the site to the central lab should be on a monthly basis. To the extent possible, the site should send each aliquot to the central laboratory separately. If a study site does not have the facility to store aliquots at the conditions specified, then they will maintain the sample on dry ice at the site and ship on dry ice on the day of collection. The central lab will ship one aliquot of the samples on dry ice to the analytical laboratory. The remaining aliquots must be kept at the central lab as a backup sample. Remaining samples will only be disposed of after approval by the global study lead (typically 6 to 12 months after the clinical study report [CSR] is published).

All blood samples will be taken by direct venipuncture. The actual sample collection date and exact time of collection will be entered on the Blood collection for IG eCRF or the unscheduled blood collection for IG eCRF, as appropriate. Sampling problems will be noted in the 'Reason sample not taken' section of the eCRF.

A laboratory manual will be provided by the central laboratory with detailed information on sample collection, sample handling and shipment.

Tubes and labels will be provided by the central laboratory with study/sample type and sample number preprinted on the label.

Further details on labeling of the IG samples can be found in [Appendix 4, Section 16.1.1](#)

6.5.5 Electrocardiogram (ECG)

A standard 12-lead ECG will be performed as indicated in [Table 6-1](#). At each visit when an ECG is done, the investigator must review and initial the tracing. The tracing must then be stored with the subject's source documents.

All ECGs must be performed on the ECG machines provided to the study site. All ECGs will be independently reviewed by a central reader. Instructions for the collection and transmission of the ECGs to the independent reviewer will be provided in the ECG investigator manual.

Even though there is no exclusion criterion specifically based on the ECG, clinically significant findings from the ECG assessment made at Week 52 of the core study must be discussed with the Novartis Medical Monitor prior to enrolling the subject in the extension study.

If the ECG findings are clinically relevant and would prevent the subject from participating in the study (taking into account the subject's overall status as well as the medication profile), the subject should not receive study treatment.

6.5.6 Pregnancy and assessments of fertility

A serum β -hCG test will have already been performed on all women of child-bearing potential who entered studies CAIN457A2304 and CAIN457A2307.

All women of child-bearing potential who are eligible to participate in this extension study will have a local urine pregnancy test as indicated in [Table 6-1](#). If positive, they will undergo a serum pregnancy evaluation conducted at the Central Laboratory

Any woman whose resulting pregnancy test is positive (based on serum β -hCG as defined by the Central Laboratory) at the Enrollment Visit Week 52 will have to discontinue from this extension study and return to the follow-up assessments in the core study.

A positive urine pregnancy test during the treatment periods of the study requires immediate interruption of study treatment until serum β -hCG is performed and found to be negative. If the serum β -hCG test is positive, the subject must be discontinued from the trial (as per [Section 5.5.10](#))

